## JHM IRB - eForm A – Protocol

- Use the section headings to write the JHM IRB eForm A, inserting the appropriate material in each. If a section is not applicable, leave heading in and insert N/A.
- When submitting JHM IRB eForm A (new or revised), enter the date submitted to the field at the top of JHM IRB eForm A.

\*\*\*\*\*

### 1. Abstract

- a. Provide no more than a one page research abstract briefly stating the problem, the research hypothesis, and the importance of the research

Monitored anesthesia care with procedural sedation has increased dramatically over the past 15 years, driven by increased utilization in gastrointestinal endoscopy, cardiology (both interventional and electrophysiology), and interventional radiology. Despite the increase in the number of patients receiving procedural sedation, current monitors of respiratory depression are inadequate to determine the degree of anesthetic induced hypoventilation. Underappreciated hypoventilation puts patients at risk for hypoxia, respiratory arrest, cardiopulmonary arrest, and other adverse events. While pulse oximetry is an outstanding and required monitor of oxygen saturation, it is a poor monitor of ventilation in patients receiving supplemental oxygen. The American Society of Anesthesiologists Monitoring Standards recognizes the underlying contribution of hypoventilation to hypoxia and adverse events by mandating the use of end-tidal capnography for procedural sedation. While well intentioned, end-tidal capnography is helpful in determining respiratory rate, it appears to be insufficient for detection of hypoventilation during procedural sedation. In fact the quantitative value may paradoxically decrease as the degree of hypoventilation increases. Further, the mechanism of anesthetic induced hypoventilation during monitored anesthesia care with procedural sedation is not entirely understood or appreciated.

Fortunately, other FDA approved monitors are available that can non-invasively monitor additional respiratory parameters and hypoventilation. The ExSpirom™ respiratory monitor is an FDA-cleared device that allows acquisition of quantitative values of respiratory rate (RR) tidal volume (TV), and minute ventilation (MV), and has a signature pattern to identify episodes of airway obstruction (Respiratory Motion, Inc. Waltham, MA). Transcutaneous CO2 (PtcCO2) monitoring is a non-invasive method for continuous monitoring of overall ventilation that closely approximates arterial carbon dioxide values (PaCO2) obtained from blood samples (SenTec, Bern, Switzerland). Further, processed electroencephalography (EEG) using bispectral index (BIS) is a non-invasive monitor that has been described as a marker for depth of anesthesia during general endotracheal anesthesia GETA and procedural sedation (Medtronic, Minneapolis, MN). Together, these devices will allow a more

precise understanding of the respiratory effects of monitored anesthesia care and procedural sedation.

This study will use this innovative combination of respiratory monitors to better understand the magnitude and mechanism of respiratory depression during MAC with procedural sedation at different anesthetic levels. For example, we will be able to distinguish the decrease in minute ventilation due to loss of motor tone and subsequent airway obstruction from that caused by decreased respiratory drive minute ventilation due to changes in tidal volume, respiratory rate, or both. Likewise, these devices have the potential to improve the monitoring of respiration and the quantification of hypoventilation, making it a potentially valuable tool for clinical care in the future, as well as further studies to determine anesthetic regimens that may cause less respiratory depression. Further, if the addition of CPAP does in fact alleviate obstruction and decrease hypoventilation, it is a potentially very important finding for patient care.

In addition, this study aims to explore a novel mechanism that may account for individual variability in the respiratory response to anesthesia. Short chain fatty acids are produced by the gut microbiome (non-pathological bacteria in the gastrointestinal tract). Low levels of these compounds have been associated with hypertension and obesity, as well as hypertension in people with sleep apnea. Receptors that are activated by these compounds are found in high concentration in the carotid body, where their activation appears to stimulate respiration. We will measure serum levels of short chain fatty acids, and hypothesize that lower concentrations will be associated with greater anesthesia induced respiratory depression and higher levels will be protective. If short chain fatty acids are shown to be associated with a protective affect on respiratory depression, this could open the door to an entirely new understanding of the mechanisms that contribute to respiratory depression during anesthesia, but also those involved with obstructive sleep apnea. In addition, it could raise the possibility that short chain fatty acids could be administered as a protective treatment.

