protective. Olfactory receptors located in vascular endothelium are activated by short chain fatty acids, causing smooth muscle relaxation, vasodilation, and protection from hypertension, with some feedback mechanisms that may prevent significant hypotension as well. Interestingly, these receptors are also highly expressed in the carotid body, where activation by short chain fatty acids increases respiratory drive. This is an intriguing possible mechanism for individual variability in susceptibility to anesthesia induced hypoventilation and may also be a contributing mechanism for hypoventilation in patients with sleep apnea. We hypothesize that lower serum concentration of short chain fatty acids will be associated with more respiratory depression and higher levels will be protective. Further, we suspect that patients with known obstructive sleep apnea, hypertension, and high BMI will have lower short chain fatty acid levels.

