This study is a randomized controlled trial comparing oxygen delivery by nasal mask with CPAP versus standard care (nasal cannula or standard facemask) during propofol-based sedation for GE procedures to reduce the incidence of hypoxia. The primary outcome will be the rate of oxygen desaturation below 90% for  $\geq 15$  seconds. In addition, secondary measures will include evaluation of mechanism and degree of respiratory depression associated with hypoxia and hypoventilation by characterizing changes in minute ventilation, tidal volume, and respiratory rate as well as the rate and degree of airway obstruction. We hypothesize that the addition of Nasal CPAP in the intervention arm will lead to decreased obstruction as positive pressure will stent open the obstructed airway. Depth of anesthesia will be monitored by BIS and we hypothesize that the degree of hypoventilation, obstruction, and will be significantly lower in the intervention arm compared to the control arm. Further, the depth of anesthesia will be independent of total propofol dose received. While the primary outcome in this study is hypoxia, we also seek to marry ETCO2 with minute ventilation and transcutaneous CO2 to better understand the total effects of sedation on respiration. Thus, the study will also serve to evaluate which mode(s) of respiratory monitoring might be the best possible intervention to enhance safety during procedural sedation. Further, we suspect that the amplitude of ETCO2 will not predict the degree of respiratory depression seen with other monitors. In addition, we will measure serum short chain fatty acid concentrations as a predictor and possible mechanism for differences in individual variability in anesthesia induced respiratory depression.

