## 7. Study Statistics

### a. Primary outcome variable.

The primary outcome will be the rate of hypoxia below 90% for  $\geq 15$  seconds.

- ### b. Secondary outcome variables. Secondary outcomes will include change in respiratory parameters (tidal volume, respiratory rate, minute ventilation, obstructive events), hypoventilation by TcCO2, EtCO2, and depth of anesthesia by BIS, as well as demographic differences. Demographic information to the occurrence of hypoxic events will be analyzed with logistic regression.

Statistical plan including sample size justification and interim data analysis.

Power analysis is based on a previous German study in the literature, of patients undergoing upper and lower endoscopy with hypoxia rates of 13.5% with standard care and 1.8% with application of nasopharyngeal airway. Using these figures to perform a power analysis for the primary outcome of hypoxia below 90%, with alpha 0.05 and power of 0.9, approximately 109 subjects in each arm or a total of 218 subjects will be needed. In order to obtain 109 completed subjects in each arm and to allow for those participants with incomplete datasets (e.g. monitor failure), we will enroll 120 subjects in each arm and a total of 240 subjects.

Frequency data will be analyzed with Fisher's Exact Test, ordered categorical data will be analyzed with the rank sum test, and continuous data will be analyzed with regression or equivalent techniques. Therefore, our primary outcome as to the incidence of hypoxia in each arm of the study will be determined using Fisher's exact test. All time series data from multiple sources will be aligned using the associated time stamp with the aid of the program data manipulation capabilities in Mathematica 11. Longitudinal analysis will be performed using a mixed model approach, initially with random intercepts alone, with the addition of nonlinear terms and interaction as indicated by the resulting model. Throughout, findings will be considered significant for  $p < 0.05$  and  $p$  values will be determined using two-sided tests. Statistical analysis will be performed with the aid of Stata 13. An analysis will be performed after the first 20 subjects to ensure complete data collection and to run a batched analysis of SCFA to evaluate this aim. An interim data analysis will be done after ~120 subjects have been enrolled.

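### The longitudinal mixed model names no patient-specific depth slope, so if patients differ in response, its interval for the depth-ventilation slope is too narrow and covariate-by-BIS tests can reject well above 5%

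*Combined protocol and SAP*

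**What the plan says.** Three places present differences between patients as something to be explained. The Abstract states that "this study aims to explore a novel mechanism that may account for individual variability in the respiratory response to anesthesia". Section 3 (Background) says of the SCFA pathway: "This is an intriguing possible mechanism for individual variability in susceptibility to anesthesia induced hypoventilation". Later in the same section SCFA is called a predictor and "possible mechanism for differences in individual variability in anesthesia induced respiratory depression".

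Aim 2 in section 2 sets out to relate ventilation to sedation depth, among other things. Section 3 names BIS as the marker of state.

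Section 7 describes one longitudinal analysis, a mixed model fitted "initially with random intercepts alone, with the addition of nonlinear terms and interaction as indicated by the resulting model". It names no random slope for depth or time, and no robust or cluster variance. It does not assign this model to Aim 4 and writes no SCFA-by-depth test. The only analysis text specific to SCFA is a batched run after the first 20 subjects. Section 7 also offers ordinary regression for continuous data.

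**The concern.** A random intercept lets patients differ in level. It gives every patient the same change in ventilation per unit of BIS. Nonlinear terms and interactions, read in the usual way as fixed effects, do not alter that. The stated path therefore never reaches a model in which patients differ in how steeply ventilation falls with depth, which is one natural meaning of variability in response.

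Two results are exposed if slopes vary:

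- **The average depth-ventilation slope (Aim 2).** Its precision is limited by the number of patients, but the model computes its standard error as if only epoch-level noise mattered.
- **Any patient-level covariate crossed with BIS.** This compares slopes between patients, so the same standard error is too small. SCFA is the obvious candidate; randomized arm would be another. Interactions kept because the fitted model indicates them would be selected using those same standard errors.

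This is separate from serial correlation, because it arises even when errors are independent. The Abstract says a positive SCFA finding could raise the possibility of giving SCFA as treatment, so a spurious modifier would not be harmless.

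**Working it through.** **The plan's own figure.** The plan gives no figure for the mixed model. Its sample size supplies the number of patients, so that is reproduced first. Inputs from section 7: "hypoxia rates of 13.5% with standard care and 1.8% with application of nasopharyngeal airway", "with alpha 0.05 and power of 0.9", and p "values will be determined using two-sided tests". With mean rate (0.135 + 0.018)/2 = 0.0765 and difference 0.117, the pooled two-proportion formula is

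n = [1.96·√(2·0.0765·0.9235) + 1.2816·√(0.135·0.865 + 0.018·0.982)]² / 0.117² = (0.737 + 0.470)² / 0.01369 ≈ 106.4, or 107 per arm.

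The plan states "approximately 109 subjects in each arm or a total of 218 subjects will be needed". That is within 2 per arm, and exact Fisher power at 109 per arm is 0.908. I therefore use N = 218.

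**Variance of the slope.** Let a patient's true slope have SD τ_b, residual SD σ, within-patient BIS SD s and m epochs. The patient's estimated slope has variance σ²/(m·s²) + τ_b². A random-intercept model counts only the first part. With τ = τ_b·s/σ:

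- true variance / model variance ≈ 1 + m·τ²
- rejection of a null covariate-by-BIS term ≈ 2Φ(−1.96/√(1 + m·τ²))
- coverage of the nominal 95% interval for the average slope ≈ 1 minus that value

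The number of patients does not enter the ratio, so enrolling more does not cure it.

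**Assumed inputs (none is in the documents).** σ = 15 points of baseline minute ventilation; s = 12 BIS units; mean slope 8 points per 10 BIS units; slope SD 1 to 3 points per 10 BIS units; 20 to 120 epochs; independent errors; SCFA unrelated to slope. Hence τ = slope SD × 1.2/15, which is 0.08, 0.16 and 0.24 for SD 1, 2 and 3.

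| Slope SD | Epochs | 1 + mτ² | Rejection: formula | Rejection: simulated | Coverage: formula | Coverage: simulated |
|---|---|---|---|---|---|---|
| 1 | 60 | 1.384 | 9.6% | 9% | 90% | 90% |
| 2 | 20 | 1.512 | 11% | 11% | 89% | 90% |
| 2 | 60 | 2.536 | 22% | 20% | 78% | 78% |
| 3 | 60 | 4.456 | 35% | 37% | 65% | 66% |
| 3 | 120 | 7.912 | 49% | 50% | 51% | 52% |

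The simulated columns use 1,000 runs per setting. A repeat simulation of these settings gave 10% to 47% rejection and 51% to 89% coverage. Full mixed models at slope SD 3 and 60 epochs (150 runs) rejected in 37% with random intercepts only and in 6.7% with a random slope added.

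**Check on a unit-free scale.** N = 218, m = 30, 1,000 runs per setting:

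| τ | Interaction, random intercept: formula | Interaction, random intercept: simulated | Per-patient slopes on covariate: simulated | Covariate main effect, random intercept: simulated |
|---|---|---|---|---|
| 0 | 5.0% | 5.6% | 5.5% | 5.6% |
| 0.1 | 8.6% | 9.8% | 6.6% | 4.9% |
| 0.2 | 18.6% | 19.2% | 5.0% | 5.9% |
| 0.3 | 30.8% | 28.6% | 5.8% | 4.0% |
| 0.5 | 50.1% | 46.3% | 4.9% | 4.5% |

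At large τ the formula runs slightly high because the fitted residual variance absorbs τ². Dividing by 1 + τ² at τ = 0.5 gives 8.5/1.25 = 6.8, and 2Φ(−1.96/√6.8) ≈ 45%. With N = 20, m = 30 and τ = 0.3, the interaction rejects in 26.4%, so the inflation is also present at the size of the early SCFA batch.

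**The case against.** The strongest reply is that the faulted interaction is not in the plan. No section writes an SCFA-by-BIS test or names the mixed model as the Aim 4 analysis. Aim 4 asks whether higher SCFA goes with lower risk of hypoventilation, obstruction and hypoxia. Those are patient-level associations, testable as main effects or with one summary per patient, and both kinds of analysis hold their error rate. If the outcome is change in minute ventilation from baseline, the random intercept already carries differences between patients in overall depression. Section 7 also describes the random-intercept model as a starting point, and every input behind the size of the effect is assumed.

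Most of this stands. A reader might infer that Aim 4 cannot be answered by the stated model, or that the plan's SCFA test rejects far too often. The documents support neither reading: Aim 4's hypotheses have unaffected routes, the interaction is only something the extension rule would permit, and the inflation depends on slope variation that the documents do not quantify.

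Two things survive. The extensions listed after the starting model do not include a random slope, so the word signalling a first step does not supply one. And the Aim 2 relation between depth and ventilation does not depend on any SCFA interaction: its interval is too narrow under the same condition, one the protocol itself makes plausible by presupposing individual variability.

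**Conclusion.** The point holds conditionally. As written, section 7 gives a model and an extension path that never let patients differ in their depth-ventilation slope. If slopes vary, the Aim 2 average slope gets an interval that is too narrow, and patient-level covariate-by-BIS interactions get p-values that are too small. Under the assumed inputs, with slope SD from 1 to 3 points per 10 BIS units and 20 to 120 epochs, false rejection is about 10% to 50% and coverage of the 95% interval about 50% to 90%. With no slope variation both are nominal. Slope SD, residual SD, BIS spread and epochs per patient are assumptions, so the range shows sensitivity and is not a forecast. SCFA main effects, analyses with one value per patient, and the randomized Fisher comparison of hypoxia are untouched.

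**What to change.** In section 7, state that:

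- models relating minute ventilation, tidal volume, respiratory rate or TcCO2 to BIS will include a patient random intercept and a patient random BIS slope;
- if such a model does not converge, per-patient slopes will be regressed on the covariate, or cluster-robust standard errors will be used;
- any SCFA-by-depth interaction will be tested only in that model.

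The Aim 4 main-effect analyses of hypoventilation, obstruction and hypoxia should remain; the slope model does not replace them.

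The cost is a few lines of text, with the same data and software. Intervals become somewhat wider, and correct. Some convergence work may be needed. The epoch length must be defined, and for TcCO2 the definition should allow for the lag of 30 seconds to 2 minutes given in section 3.

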## **2. Objectives (include all primary and secondary objectives)**

Specific Aim 1: To test whether nasal CPAP reduces the incidence of hypoxia during procedural sedation with propofol as compared to usual care. Hypothesis: A randomized clinical trial of an intervention to reduce airway obstruction (nasal CPAP) will decrease the incidence of hypoxic events ( $<90\% \geq 15s$ ) compared to usual care in patients undergoing procedural sedation.

Specific Aim 2: To determine the duration, magnitude and mechanism of hypoventilation and its association with hypoxia in subjects undergoing procedural sedation. Hypothesis: By determining minute ventilation, transcutaneous CO2 and sedation depth while measuring end-tidal CO2, it will be possible to relate ventilation to hypoxic events, sedation depth and airway obstruction. Further, reductions in the incidence of hypoxia in the intervention group will be consistent with the hypothesis that loss of airway motor tone underlies hypoventilation and associated hypoxia.

Specific Aim 3: To characterize the physiologic state when end-tidal capnography is insufficient for detecting hypoventilation. Hypothesis: The amplitude of the capnographic signal is not representative of the adequacy of ventilation due to artifact from loss of airway motor tone during procedural sedation.

Specific Aim 4: To determine if there short chain fatty acid serum concentration is protective for procedural sedation induced hypoventilation, obstruction and hypoxia: Hypothesis: Higher concentration

of short chain fatty acids will be reduce the risk of hypoventilation, obstruction, and hypoxia and suggests a link between respiratory function and gut microbiome.

**3. Background** (briefly describe pre-clinical and clinical data, current experience with procedures, drug or device, and any other relevant information to justify the research)

There has been an explosion in the number of anesthetics administered outside of traditional operating rooms in the last decade. The rise in such non-operating room anesthetics (NORA) has been driven by increased demand in gastrointestinal endoscopy (GE), interventional radiology, and cardiology. Increased anesthesia support for GE procedures appears to be the primary driver for the rise in NORA. The increase is huge – between 2003 and 2009, anesthesia support for GE for Medicare patients grew from 13.5% to 30.2%, while anesthesia support for patients undergoing GE procedures with private insurers increased from 13.6% to 35.5%. In 2009, an estimated 18.6 million gastrointestinal endoscopies were performed in the United States, of which 6.9 million were upper, 11.5 million lower, and 228,000 biliary. Together, these studies suggest that more than 6 million anesthetics were administered for GE in 2009. Further, previous projections have indicated that anesthesia services would be used in over half of all GE procedures by 2015. These predictions appear to be reflected in reports of increased NORA for GE at tertiary medical centers. In the endoscopy suite at the Johns Hopkins Hospital, nearly all GE procedures are performed with anesthesia involvement, with an increase in annual cases from from approximately 4000 in 2007 to nearly 12,000 in 2015.

Fundamentally, the shift to anesthesia involvement in gastrointestinal endoscopic procedures represents a change from gastroenterologist directed, nurse administered sedation with fentanyl and midazolam, to a propofol-based anesthetic. This change has been driven by several factors, including patient preference and satisfaction, risk aversion on the part of the proceduralist, perception of better procedural conditions, and evidence of decreased length of stay in the post anesthesia care unit and faster throughput. The use of propofol sedation compared to midazolam and fentanyl appears to be associated with deeper levels of anesthesia. In fact, when propofol is used for procedural sedation, electroencephalographic monitoring such as BIS suggests anesthetic depth often associated with general anesthesia. Some retrospective studies have suggested higher rates of complications with propofol-based anesthetics compared to midazolam and fentanyl, including cardiorespiratory arrest, aspiration, and hypoxia. In contrast, other studies have suggested no difference or improved outcomes with anesthesia involvement, and patients were generally sicker with longer cases.

The large and growing number of GE procedures with anesthesia services underlies the importance of delivering safe care, as even a low rate of sedation related adverse events may affect a large number of patients. In several retrospective studies, cardiopulmonary events occurred in up to 11.7/1000 events, and hypoxia was the most common. While the full implication of mild transient hypoxia on outcomes is unknown, significant hypoventilation with hypercarbia and hypoxia commonly proceeds cardiopulmonary arrest. Respiratory depression from oversedation is an important mechanism of patient injury during monitored anesthesia care. The rate of hypoxia is considered as a marker for unsafe sedation practices in endoscopy suites. However, the true rate of hypoxia associated with sedation for endoscopic procedures is unknown and ranges from 1% to 70% in the literature. The variability may be related to adequacy of surveillance as well as differences in the definition of hypoxia. For instance, lower rates of hypoxia in manually and electronically recorded pulse oximetry data during clinical care have been reported. A recent study from the Netherlands reported a hypoxia rate in average risk patients during sedation for colonoscopy without oxygen supplementation of 55.6%. A recent study from Germany pseudorandomized patients undergoing upper, lower, or combined endoscopic procedures with propofolbased anesthesia to nasal cannula alone or with a nasopharyngeal airway and found rates of

hypoxia of 1.8% versus 13.5%. In another study from the Cleveland Clinic evaluating the STOP-BANG sleep apnea scoring system, subjects with STOP-BANG score >3 had a rate of hypoxia of 16.9% versus 11.2% in the STOP-BANG score <3 group, but this did not reach significance in this underpowered study. However, higher BMI was associated with more sedation-related adverse events (SRAE).

Hypoxia is related to both centrally mediated changes in respiratory drive caused by sedative drugs, direct effects of the anesthetic agents on motor function, and diminished airway tone due to sleep or sedation (change in state). Furthermore, sedative agents decrease airway tone and increase the risk of obstruction, while blunting the normal arousal that occurs in response to hypercarbia and hypoxia during obstruction events during natural sleep. Obstructive sleep apnea and obesity are risk factors for airway obstruction during sedation. Use of nasal CPAP has been demonstrated to improve ventilation, alleviate upper airway obstruction, and reverse hypoxia in women undergoing spinal anesthesia with sedation for gynecological procedures. Continuous positive pressure stents the airway, alleviating the obstruction from oropharyngeal soft tissue that occurs during sleep and under sedation, and has been advocated in patients with obstructive sleep apnea on CPAP at home. Positive pressure ventilation using a nasal mask has also been shown to be effective. The Supernova mask (RMD medical, Tucson, AZ) is FDA approved commercially available nasal mask that can be attached to a standard anesthesia circuit or Jackson Reese, and allows for up to 30 l/min of oxygen delivery, making it convenient for use in procedural sedation. It can supply CPAP as well as supplemental positive pressure breaths by closing the mouth or applying gentle cephalad directed submandibular pressure to push close the oropharynx by approximation of the tongue and palate.

During general endotracheal anesthesia (GETA), airway obstruction is bypassed by the endotracheal tube and the closed system allows for minute ventilation to be continuously monitored and end tidal carbon dioxide (EtCO2) generally approximates arterial carbon dioxide (PaCO2). During monitored anesthesia care, end tidal carbon dioxide (EtCO2) monitoring is routinely utilized as a qualitative marker of respiratory rate, but quantitative evaluation to identify hypoventilation is usually not possible by nasal cannula or standard mask ("green mask). Likewise, minute ventilation is not routinely monitored. In fact, ETCO2 reading often decreases during hypoventilation with opioids and sedatives, while respiration paradoxically decreases (see figure, attached). Still, ETCO2 monitoring remains an important measure of respiratory rate, and has been shown to decrease the rate of hypoxia during procedural sedation for colonoscopy from 32% to 18%. Prevention of hypoxia by administering supplemental oxygen may blunt the potential increase in respiratory drive stimulated during opioid and sedative administration. However, prevention of hypoxia during procedural sedation using oxygen allows for airway interventions prior to the onset of hypoxia when ventilation is being carefully monitored. Current standard of care for monitored anesthesia care with sedation includes use of qualitative EtCO2 as a marker of respiration, but does not include quantitative monitoring of minute ventilation or the degree of hypoventilation.

Impedance based respiratory volume monitoring has been used to assess adequacy of ventilation and airway obstruction in patients undergoing endoscopic gastrointestinal procedures. In fact, such studies also suggest that EtCO2 often decreases as minute ventilation decreases. In this study, changes in minute ventilation from baseline, and episodes of upper airway obstruction will be assessed using the commercially available ExSpiron™ (Exspiron, Respiratory Motion Inc, Waltham MA). Previous studies using the ExSpiron™ have suggested that decreased minute ventilation during sedation for GE procedures is primarily due to decreased tidal volume rather than respiratory rate. Transcutaneous carbon dioxide has proven to closely approximate to arterial carbon dioxide (PaCO2), and in fact more closely reflects PaCO2 than end tidal carbon dioxide (EtCO2). Transcutaneous carbon dioxide (TcCO2) has been shown to closely correlate with PaCO2. After approximately 5 minutes of calibration time, it appears to track changes in PaCO2 with a lag time of 30 seconds to 2 minutes. In our experience using the TcCO2 monitor

for clinical application during jet ventilation, we have found the device to consistently track within 5 points of the PaCO2. (Sentec, Therwil, Switzerland).

Depth of anesthesia using processed electroencephalography has been described as a marker for depth of anesthesia during GETA and MAC with sedation. Depth of anesthesia using bispectral index (BIS) has been relatively well established and is known to correlate well with other measures of depth of anesthesia. We will use bispectral index (BIS) (Medtronic, Minneapolis, Minnesota) as a marker of state. In addition, all clinical data utilized in routine practice will be recorded, including drug dosing, method of drug administration, and length of stay in the recovery area.

Recently, alterations in the gut microbiome have been implicated in obesity, hypertension, obstructive sleep apnea induced hypertension, and airway smooth muscle tone that may relate to reactive airway disease. In general, lower short chain fatty acid levels are associated with pathology, and higher levels appear to be

protective. Olfactory receptors located in vascular endothelium are activated by short chain fatty acids, causing smooth muscle relaxation, vasodilation, and protection from hypertension, with some feedback mechanisms that may prevent significant hypotension as well. Interestingly, these receptors are also highly expressed in the carotid body, where activation by short chain fatty acids increases respiratory drive. This is an intriguing possible mechanism for individual variability in susceptibility to anesthesia induced hypoventilation and may also be a contributing mechanism for hypoventilation in patients with sleep apnea. We hypothesize that lower serum concentration of short chain fatty acids will be associated with more respiratory depression and higher levels will be protective. Further, we suspect that patients with known obstructive sleep apnea, hypertension, and high BMI will have lower short chain fatty acid levels.

This study is a randomized controlled trial comparing oxygen delivery by nasal mask with CPAP versus standard care (nasal cannula or standard facemask) during propofol-based sedation for GE procedures to reduce the incidence of hypoxia. The primary outcome will be the rate of oxygen desaturation below 90% for  $\geq 15$  seconds. In addition, secondary measures will include evaluation of mechanism and degree of respiratory depression associated with hypoxia and hypoventilation by characterizing changes in minute ventilation, tidal volume, and respiratory rate as well as the rate and degree of airway obstruction. We hypothesize that the addition of Nasal CPAP in the intervention arm will lead to decreased obstruction as positive pressure will stent open the obstructed airway. Depth of anesthesia will be monitored by BIS and we hypothesize that the degree of hypoventilation, obstruction, and will be significantly lower in the intervention arm compared to the control arm. Further, the depth of anesthesia will be independent of total propofol dose received. While the primary outcome in this study is hypoxia, we also seek to marry ETCO2 with minute ventilation and transcutaneous CO2 to better understand the total effects of sedation on respiration. Thus, the study will also serve to evaluate which mode(s) of respiratory monitoring might be the best possible intervention to enhance safety during procedural sedation. Further, we suspect that the amplitude of ETCO2 will not predict the degree of respiratory depression seen with other monitors. In addition, we will measure serum short chain fatty acid concentrations as a predictor and possible mechanism for differences in individual variability in anesthesia induced respiratory depression.

